23.02.2021

**COMPARISON OF GLIDESCOPE® TITANIUM
(VERATHON) AND FLEXIBLE INTUBATION VIDEO
ENDOSCOPE® (FIVE, STORZ) IN TERMS OF
INTUBATION SUCCESS IN INFANTS WITH PIERRE
ROBIN SEQUENCE**

[name]

[name]

[name]

MATERIAL – METHOD

Our study is a prospective randomized controlled trial. Intubation success and intubation times were compared with Flexible Intubation Video Endoscope (FIVE)® or GlideScope® Titanium devices in patients with Pierre Robin Sequence. Hacettepe University Clinical Research Ethics Committee (Date: 23.02.2021, Decision No: 2021/4-16 KA-20115) and Turkish Medicines and Medical Devices Agency (TITCK) approval letter was obtained (Number; E-688699933-511.06- 365554).

Patients with Pierre Robin Sequence who were younger than 12 months and underwent elective surgery under general anesthesia between March 2021 and December 2023 were included in the study. Patients requiring emergency surgery, patients requiring rapid sequence intubation, patients who had already been intubated or tracheostomized to the operating room, patients who would not be operated on under general anesthesia, patients who did not have family consent and who could not provide informed consent were excluded from the study. Randomization was performed by a research assistant using a computer to generate random numbers 1 and 2 and was terminated when the minimum number of patients in each group was reached. Number 1 was assigned to the GlideScope® Titanium and number 2 was assigned to the Flexible Intubation Video Endoscope® (FIVE). Both devices are routinely used successfully as the first choice in this patient group in our clinic. Randomization was concealed in a sealed envelope from the operator and the operator was informed after parental consent to participate in the study was obtained. Endotracheal intubation was performed by 2 faculty members who were experts in the field. Since faculty members would not know the assigned intubation device before the patient was taken to the operating room, both devices were kept ready in the room. In randomized patients, GlideScope® Titanium (Verathon) or Flexible Intubation Video Endoscope® (FIVE) 11301 abx, 2.85 mm (Storz) devices were compared in terms of intubation success as the primary outcome and our specified secondary outcome measures.

After patients were monitored with routine monitoring (SpO₂, noninvasive blood pressure, ECG, pulse), induction was applied in accordance with the clinical experience of the operator and intubation was started with the endotracheal tube selected in accordance with the clinical experience of the relevant operator. As a standard in our center, patients with Pierre Robin Sequence are taken to the operating room without premedication in order to avoid possible respiratory complications. Before anesthesia induction, vascular access is evaluated, and if appropriate, vascular access is established with a 24-26 Gauge IV cannula before induction or following induction according to the preference of the responsible anesthesiologist. Before anesthesia induction, preoxygenation with 100% oxygen is routinely applied and apneic oxygenation is applied with various techniques appropriate for the patient at all stages of the procedure. In anesthesia induction, 8% sevoflurane, 1 mg/kg methylprednisolone, 0.8-1.0 mg/kg rocuronium are used in 80% oxygen - 20% air mixture. Dexmedetomidine or remifentanil infusion is preferred as analgesic. Long-acting opioids are avoided as a standard approach in this patient group. Following standard two-handed AND technique mask ventilation, intubation is performed, and the intubation technique was selected together with the randomization method specified in our study.

If GlideScope® Titanium was to be used, a 50-60° angle was applied with the appropriate stylet and the appropriate one was selected from the 3 pediatric blade sizes according to the clinical experience of the operator. If Flexible Intubation Video Endoscope® (FIVE) was to be used, the appropriate endotracheal tube was loaded into the bronchoscope and made ready. The size

and selection of the endotracheal tube to be used were not changed for the purpose of the study. The operator used the selection he/she made routinely for the patient according to his/her body weight and physical development. The number of attempts for successful intubation and the duration were recorded by an unblinded research assistant. The chronometer was started when the FFB or the videolaryngoscope started to pass through the patient's mouth/nose and the chronometer was stopped when the ventilation of the lungs was confirmed with the end tidal carbon dioxide trace and this time was recorded as the successful intubation time. The time between the FFB or the videolaryngoscope passing through the mouth/nose and the best glottic view was obtained was recorded as the best glottic visualization time. The operator reported the percentage of glottic opening score (POGO) and Cormack Lehane scores after obtaining the best glottic visualization in the Glidescope group. In accordance with standard clinical practice, the operator was allowed to perform optimal external laryngeal manipulation as required during laryngoscopy. Endotracheal tube passage time was defined as the intubation time minus the best glottic visualization time and was recorded. Failed intubation was defined as an intubation attempt exceeding 120 seconds or removal and repositioning of the airway device from the mouth/nose or esophageal intubation. If the intubation attempt exceeded 120 seconds or the patient's SpO₂ value fell below 85% and/or bradycardia occurred at any stage of the procedure, the attempt was planned to be terminated if it was ongoing and mask ventilation of the patient was provided. Airway management after unsuccessful intubation was managed in accordance with the difficult airway algorithm under the responsibility of the faculty member in charge. Complications during the attempt were recorded. Complications were determined as esophageal intubation, desaturation defined as SpO₂<90%, airway bleeding, soft tissue damage, bradycardia (heart rate below 90 beats/min), systolic hypotension (below 60 mmHg for 0-1 month, 70 mmHg for 1-12 months), dysrhythmia, and cardiac arrest. During this entire process, a difficult airway cart and sugammadex were kept ready to be applied in case of emergency. In patients who were evaluated to have complications or who might need a tracheostomy, a pediatric ENT specialist and a surgical tracheotomy set were present in the operating room. All these preparation processes and procedures are routinely applied in this manner in our clinic.

Objective secondary outcomes included intubation time (time between the passage of the FFB through the patient's mouth/nose or the video laryngoscope through the patient's mouth and the end tidal carbon dioxide trace being seen on the monitor), time to obtain the best glottic visualization, endotracheal tube passage time (intubation time - time to obtain the best glottic view), whether complications developed (esophageal intubation, desaturation, airway bleeding, soft tissue damage, bradycardia, hypotension-hypertension, dysrhythmia, cardiac arrest), CL, and POGO scores. Subjectively, ease of use, ease of placement in the oropharynx/nasopharynx, quality of vision, and ease of tube advancement were evaluated and recorded by the relevant faculty member using a 4-point Likert scale (excellent, good, moderate, poor).

Parameters recorded in the preoperative period in all patients; ✓ Age, gender, body weight, body surface area (BSA),

✓ Additional diseases, accompanying syndromes, medications used, previous surgeries, ASA (American Society of Anesthesiologists) score,

✓ Birth history, postpartum APGAR scores,

✓ Gastroesophageal reflux, feeding disorders,

✓ Preoperative airway evaluation; mouth opening (cm), thyromental distance

(cm), neck range of motion, Frontal Plane-to-Chin Distance (FPCD) measurement for evaluation of jaw retraction (cm), respiratory distress in supine position (yes/no), oxygen requirement (yes/no), hypotonia (yes/no), history of intubation-tracheostomy (yes/no), intensive care unit admission (yes/no), history of Obstructive Sleep Apnea (OSA) (yes/no), history of aspiration (yes/no), presence of laryngomalacia/tracheal stenosis (yes/no), additional physical examination findings,

✓ Results of previous bronchoscopic evaluations, if any, computed tomography imaging (cranial/thoracic), magnetic resonance imaging (cranial/thoracic), swallowing tests, echocardiography images and polysomnography

Statistical Analysis

IBM SPSS Statistics ver. 25 (IBM Corporation, Armonk, NY, USA) program was used for data analysis. Whether the distribution of quantitative variables was distributed close to normal was examined with the Shapiro-Wilk test, and whether the assumption of homogeneity of variances was met was examined with the Levene test. Descriptive statistics were expressed as median (25th percentile-75th percentile) for quantitative variables, while qualitative variables were shown as number of cases and (%). As a result of the goodness-of-fit tests, the significance of the differences between the groups in terms of variables for which the parametric test statistics assumptions were not met was examined with the Mann Whitney U test. In the analysis of categorical data, if the expected frequency was below 5 in at least 1/4 of the cells in 2x2 cross tables, the categorical data in question were evaluated with Fisher's exact probability test, and when the expected frequency was between 5-25, the Continuity Corrected χ^2 test was used. RxC (in case at least one of the categorical variables in the row or column has more than two results) in the cross tables, if the expected frequency is below 5 in at least 1/4 of the cells, the categorical data in question were evaluated with the Fisher Freeman Halton test. The results were considered statistically significant for $p<0.05$.

Power Analysis

It is not known exactly how much the difference in intubation time is significant in the clinic. There are very few studies in the literature on this subject in pediatric patients and in the patient group with PRS.

In a study conducted by Fiadjoe et al. on a pediatric PRS mannequin, GlideScope Cobalt videolaryngoscope and FFB were compared in terms of their success in the first intubation attempt and no difference was found (88.3% vs. 85%, respectively, $p=0.59$). Although there was a statistically significant difference in intubation time between the two groups, this difference was not considered clinically significant (median 30.9 s for FFB and 25.1 s for GCV, $p=0.04$). It was interpreted that significant adverse cardiopulmonary events such as arterial oxygen desaturation, bradycardia and hypotension were unlikely to occur during this period.

Again, Fiadjoe et al. In a study conducted by in a pediatric patient group, Glidescope videolaryngoscope and conventional direct laryngoscope were compared in terms of intubation success and intubation time. In this study, the significant endotracheal intubation time difference was accepted as 10 seconds. In our study, based on the existing literature studies and our clinical experience, the significant endotracheal intubation time difference was accepted as

10 seconds, and the total sample size was calculated as 46 patients, with 23 patients in each group for $\alpha=0.05$ and 90% power. Patient recruitment continued until the minimum number of patients in each group was reached.

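### Does drawing random 1s and 2s until each arm has its minimum of 23 undermine the planned 46 patients or the concealment of allocation?

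*Combined protocol and SAP*

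**What the plan says.** In the combined protocol and SAP, the Material – Method section has a research assistant produce the allocation sequence, which was made "using a computer to generate random numbers 1 and 2 and was terminated when the minimum number of patients in each group was reached". One number stands for each device. The assignment was held in a sealed envelope and disclosed to the operator after parental consent. Two faculty members performed the intubations.

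The Power Analysis section states that "the total sample size was calculated as 46 patients, with 23 patients in each group", for a 10-second difference in intubation time "for $\alpha=0.05$ and 90% power". It closes with the same stopping rule: "Patient recruitment continued until the minimum number of patients in each group was reached".

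The document describes no blocks and no pre-balanced list. It sets no cap on the total, and it does not say what happens to later draws once one arm has reached 23.

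**The concern.** Independent draws of 1 and 2 do not fill two arms at the same pace, so one arm will usually reach 23 while the other is still short. There are then two ways to finish.

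- **Keep drawing.** The total becomes random, exceeds 46 in most sequences, and the arms end unequal. Infants with an uncommon and difficult airway would be enrolled beyond the calculated number.
- **Close the full arm.** The total stays at 46, but every later infant goes to the other device. Two operators who see each device used could work this out before the envelope is opened. Easier infants could then be steered to the device still open, and the comparison would be biased at the end of the sequence.

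The text does not name the route taken. One route is harmless to validity and the other is not, so the silence looks like a design flaw.

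**Working it through.** **Inputs.** Two arms with a minimum of m = 23 each, target 46, difference 10 s, α = 0.05 and power 90% (all from Power Analysis). Assumed because not stated: probability ½ per draw, and a two-sided test.

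**1. The plan's own 46.** It cannot be reproduced directly, because no SD is given. From n = 2(1.960 + 1.282)²·SD²/10² with n = 23, the implied SD is 10·√(23/2)/3.242 ≈ 10.5 s (10.2 s with a t-test). An SD of 10 s gives 22 per arm by the normal formula and 23 by the t-test. So 46 is plausible but unverified. Steps 2 and 4 do not depend on the SD.

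**2. Keep drawing until both arms have at least 23.** For n ≥ 46, P(N = n) = 2·C(n−1, 22)/2ⁿ.

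- P(N = 46) = C(46, 23)/2⁴⁶ = 0.117.
- E(N) = 46 + 46 × 0.117 = 51.4, with SD 4.7.
- Median 50, 90th percentile 58, 95th percentile 61; P(N ≥ 52) = 40%.

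A simulation of 100,000 sequences agreed (mean 51.4).

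**3. What the overshoot costs the comparison.**

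- Efficiency relative to equal arms of the same total is 4·n₁·n₂/(n₁ + n₂)². At 23:28 it is 2576/2601 = 99%. At the 95th percentile, 23:38, it is 3496/3721 = 94%.
- Power at 23:28 with the implied SD: SE = 10.46 × √(1/23 + 1/28) = 2.94; 10/2.94 − 1.96 = 1.44; power about 92%, against 90% at 23:23.
- Before each draw the chance of either device is still ½. By construction the last patient falls in the arm that ends at exactly 23, but nobody knows before the draw that this patient will be the last.

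**4. Close an arm at 23 and hold the total at 46.** The draw at which the first arm fills follows the same expression for n = 23 to 45, and the number of forced allocations is 46 − n.

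- Mean 5.4 of 46 (12%), median 5, never fewer than 1.
- P(at least 5) = 53%; P(at least 10) = 13%.

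**5. The usual alternatives.** With k patients per arm in a list or block of known size, the expected determined tail is 2k/(k + 1).

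- Blocks of 4 (k = 2): 4/3 of 4, or 33%.
- Blocks of 6 (k = 3): 3/2 of 6, or 25%.
- One shuffled list of 46 (k = 23): 46/24 = 1.9 of 46, or 4%.
- The rule read literally: 0%.

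Randomly varying block sizes lower the block figures but do not bring them to zero when operators are unblinded.

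**The case for a change.** The strongest argument for acting is that a reader cannot tell from the text which route was taken. The two operators performed every case and saw each device, and an unblinded assistant recorded the attempts and times. If an arm was closed, five or so forced allocations out of 46 are not negligible, and a sealed envelope cannot hide an assignment that follows from a running count.

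Part of this stands: the document is silent on how a full arm was handled. The rest is conditional. Neither section says that an arm was closed or that infants were diverted. To exploit a closed arm, the two operators would have to pool their counts, know that the arm was full, and influence who was enrolled. The document gives the operators no role in screening or consent. Even then the great majority of allocations, about 88% on average, would remain concealed.

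The claim that infants were enrolled beyond need is also weak. The 46 was derived for intubation time, a secondary outcome. No requirement is given for the primary outcome, intubation success, so nothing shows that 51 is too many. The infants were having elective surgery in any case, and the document describes both devices as routine first choices at the centre.

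Permuted blocks would fix the total, but they make more assignments guessable than the rule as written. A single shuffled list of 46 would do better than blocks. Neither can be adopted now, because the text is in the past tense and covers patients treated from March 2021 to December 2023.

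**Conclusion.** No change to the plan follows. The arithmetic behind the concern is right, assuming equal probability per draw: exactly 46 occurs in 11.7% of sequences, the expected total is 51.4, and about 5.4 allocations would be forced if an arm were closed. The conclusion drawn from it does not hold. A minimum of 23 per group permits a larger total, so no stated figure is contradicted. As written, the rule is valid and unpredictable, its stopping does not depend on outcomes, and at the expected split it costs about 1% in efficiency while power rises slightly. The bias argument needs a rule that the document does not contain.

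The gap is one that the trial report fills in the ordinary way, by giving the arm sizes reached. These are informative: unequal arms with the smaller at 23 fit the literal rule, while exactly 23:23 would be expected only 11.7% of the time and would justify asking how the sequence was completed. Only if allocations turned out to have been forced would an analysis without them be worth having.

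### The primary outcome, intubation success, gets only counts and a p-value: the plan gives no effect estimate, confidence interval, power or precision for it, and the one sample-size calculation is for a secondary outcome

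*Combined protocol and SAP*

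**What the plan says.** Material – Method makes success primary: the "devices were compared in terms of intubation success as the primary outcome and our specified secondary outcome measures". The paragraph on secondary outcomes in the same section begins "Objective secondary outcomes included intubation time", so time is secondary.

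Power Analysis works only with time. Its target is a gap of 10 seconds between the devices, chosen from published work and local experience. On this basis "the total sample size was calculated as 46 patients, with 23 patients in each group", with alpha set at 0.05 and power at 90%. That section also reports first-attempt success of 88.3% and 85% in a mannequin study, but as background. No target difference, power or precision for success is derived from those rates.

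Under Statistical Analysis, "qualitative variables were shown as number of cases and" percentages. The 2x2 test is Fisher's exact "if the expected frequency was below 5 in at least 1/4 of the cells in 2x2 cross tables" and the continuity-corrected chi-square for larger expected counts. The decision rule is "The results were considered statistically significant for" p<0.05. Neither section mentions a difference or ratio of proportions, or a confidence interval.

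**The concern.** The stated 90% power belongs to a secondary outcome. For the primary outcome the reader is told neither how large a difference the trial could detect nor how precisely it would be estimated. The planned output is two percentages and a p-value.

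This matters most if the result is non-significant. Material – Method says "Both devices are routinely used successfully as the first choice in this patient group in our clinic", so success may well be high in both arms. A p-value above 0.05 would then be compatible both with near-equal success and with one device failing considerably more often. In infants with difficult airways those are different conclusions, and nothing in the planned analysis of the primary outcome tells them apart.

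**Working it through.** **1. The plan's own figure (time).** The usual formula is n per arm = 2(z₀.₉₇₅ + z₀.₉₀)²(SD/Δ)², with Δ = 10 s from Power Analysis. Here 2 × (1.960 + 1.282)² = 21.01, so n = 21.01 × (SD/10)². No SD is given, so 23 cannot be reproduced directly. Solved backwards, n rounds up to 23 for an SD between about 10.23 s (n = 22) and 10.46 s (n = 23). A two-sided t-test calculation gives about 9.99 to 10.23 s. The 46 is therefore plausible for an SD near 10 s, and it concerns time only.

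**2. Power for success.** Inputs: 23 per arm (Power Analysis); the plan's 2x2 rule, read as Fisher if any of the four expected counts is below 5 and the continuity-corrected chi-square otherwise; two-sided 0.05 (sidedness is not stated, so assumed). True success in the better arm is assumed at 80% to 99%; 88.3% is the higher mannequin rate, used only as a point in that range. The 20-point gap is my illustration, since the plan names no important difference in success.

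Power(p₁, p₂) = Σₐ Σ_b Bin(a; 23, p₁) · Bin(b; 23, p₂) · 1[p-value(a, b) < 0.05], summed over all 24 × 24 outcomes.

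| Better arm | Lower rate giving 90% power | Gap | Power for a 20-point gap |
|---|---|---|---|
| 99% | 64.8% | 34.2 points | 47% |
| 95% | 53.8% | 41.2 points | 37% |
| 88.3% | 41.5% | 46.8 points | 28% |
| 80% | 31.0% | 49.0 points | 22% |

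At 100% versus 80%, power is 50%.

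**3. Unequal arms.** Material – Method stops randomization when each group reaches its minimum, so one arm may exceed 23. If the sequence is unrestricted with equal probabilities (an assumption), an exact 23/23 split has probability C(45,22)/2⁴⁵, about 12%. With 23 and 28 as an example, and the same range for the better arm, the gap for 90% power is 30 to 47 points. Power for a 20-point gap is 23% to 64%, depending also on which arm is larger.

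**4. Precision.** The Newcombe 95% interval for d = p₁ − p₂ combines the Wilson limits (l, u) of each arm: lower limit d − √[(p₁−l₁)² + (u₂−p₂)²], upper limit d + √[(u₁−p₁)² + (p₂−l₂)²].

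- 23/23 in both arms: the Wilson lower limit is 23/(23 + 3.84) = 0.857 and the upper is 1, giving ±0.143.
- 20/23 in both arms: Wilson 0.679 to 0.955, so √(0.191² + 0.085²) = 0.209, giving ±0.209.
- 18/23 in both arms: ±0.235.
- 22/23 versus 18/23: Fisher p = 0.187, interval −3.2 to 37.9 points.

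Over every non-significant table at 23 per arm, the larger absolute limit is never below 14.3 points.

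**5. Test against interval.** Of the 276 tables with one arm better, 15 have p ≥ 0.05 but a Newcombe interval that excludes zero. An example is 22/23 versus 17/23: p = 0.096, interval 0.3 to 42.4 points. None has p < 0.05 with an interval that includes zero.

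**The case against.** The plan misstates nothing. Power Analysis says openly that the calculation rests on time, the condition is rare, and sizing on time is a practical choice. Counts and percentages per group let any reader compute the difference and its interval. The feared misreading would be the reader's, not the plan's. The 20-point benchmark appears nowhere in the documents. Near 100% success, power for it is about a coin-flip at 23 per arm (47% to 50%), and 64% if the better arm is at 99% and has 28 infants against 23. So one cannot say in general that a non-significant result is likely.

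Most of this stands. It limits how serious the point is and requires the 20 points and the arm sizes to be flagged as assumptions. It does not remove the point. The effect estimate and interval for a primary outcome belong in the plan, not with the reader, and the 90%-power gaps of 34 to 49 points do not depend on the 20-point choice.

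Three stronger readings are tempting and not supported:

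- That the plan claims 90% power for success. It does not; the figure is tied to the 10-second difference.
- That 46 is miscalculated. The missing SD prevents a check, and an SD near 10 s gives it.
- That the trial intends to declare the devices equivalent. The documents make no such claim.

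**Conclusion.** The point holds as a low-cost improvement rather than an error that must be corrected. The primary outcome has no reported power or precision and no planned between-group estimate or interval, so a non-significant result could not by itself support similar success.

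At exactly 23 per arm, with the better arm assumed at 80% to 99%, the trial is well powered for success only against gaps of about 34 to 49 points. The 22% to 47% power for 20 points is illustrative. Even identical observed success leaves differences of 14 points (23/23) to 24 points (18/23) within the interval. Moderately unequal arms shift these figures but do not change the conclusion.

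**What to change.** Keep success as the primary outcome, the specified test and the sample size. Make two additions.

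(1) Statistical Analysis:

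> The primary effect estimate is the difference in intubation success proportions with a 95% confidence interval (Newcombe). A difference is claimed only if the specified 2x2 test gives p<0.05; a non-significant result is interpreted by the confidence limits and not as equal success.

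(2) Power Analysis:

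> The 46 patients and 90% power refer to intubation time only; no calculation is reported for intubation success. With 23 per group, 90% power for success needs a difference of about 34 to 49 percentage points (better group 99% to 80%, assumed). If one group is larger because randomization runs until each reaches its minimum, for example 23 and 28, the figure is about 30 to 47 points.

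The text describes recruitment as finished, so label both additions post hoc if they are made after outcome data were seen.

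The cost is wording and one interval calculation, with no extra patients and no new test. There are two downsides. The stated sensitivity for the primary outcome becomes much less favourable. The interval can also disagree with the test in a few tables, which is why the test alone decides whether a difference is claimed. Newcombe is a reasonable choice but not the only one; what matters is that the method is named.

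### Does the plan need a rule for how intubation time is counted after a failed attempt?

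*Combined protocol and SAP*

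**What the plan says.** All of this is in the combined protocol and SAP, mainly under Material – Method.

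- **Clock.** One start (device entering the mouth or nose) and one stop, when ventilation is "confirmed with the end tidal carbon dioxide trace and this time was recorded as the successful intubation time". The outcome list later in the section repeats the same two points.
- **Attempts.** "The number of attempts for successful intubation and the duration were recorded by an unblinded research assistant".
- **Failure.** "Failed intubation was defined as an intubation attempt exceeding 120 seconds or removal and repositioning of the airway device"; oesophageal intubation also counts.
- **After a failure.** If a limit is reached, "the attempt was planned to be terminated if it was ongoing and mask ventilation of the patient was provided". Then: "Airway management after unsuccessful intubation was managed in accordance with the difficult airway algorithm".
- **Derived time.** "Endotracheal tube passage time was defined as the intubation time minus the best glottic visualization time and was recorded".
- **Status.** "Objective secondary outcomes included intubation time", so the time is secondary; the primary outcome is intubation success. Power Analysis nevertheless sizes the trial on a 10 s difference in intubation time (23 per group, 90% power).
- **Failure rates.** Power Analysis cites a mannequin comparison of "success in the first intubation attempt and no difference was found (88.3% vs. 85%, respectively".

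Nothing states how the clock is handled after a failed attempt.

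**The concern.** Three readings are possible after a failure: (a) the clock runs on to the eventual carbon dioxide trace, (b) it restarts at the next insertion, (c) the time is missing. They measure different things. Under (a) a patient with a failed attempt carries that attempt and the mask ventilation in the intubation time. Tube passage time, a simple subtraction, would then contain minutes that have nothing to do with passing a tube. Under (a) or (b) the final time might also belong to a device other than the assigned one.

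Because the trial is sized on this outcome, the worry is that a reader cannot tell which quantity lies behind the reported time, and that significance could turn on an undocumented choice.

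**Working it through.** **1. Which reading does the text favour?** The single start and stop, taken literally, allow (a). Three features point to one attempt. The quantity is named as the time of the successful intubation. The 120 s limit applies to an attempt, so attempts have to be timed separately to apply it. Tube passage time carries its stated meaning only if both of its parts come from the same attempt. The text leans to (b) or (c) without settling the matter.

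**2. How many patients?** Failure rates are 1 − 0.883 = 0.117 and 1 − 0.85 = 0.15. Expected failed first attempts: 23 × 0.117 + 23 × 0.15 = 2.69 + 3.45 = 6.1 of 46. P(at least one) = 1 − 0.883^23 × 0.85^23 = 0.9986. The other 40 or so have the same time under every reading.

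**3. The plan's sample size.** No SD is given, so 23 per group cannot be reproduced independently. Solving n = 2(1.960 + 1.282)² (SD/10)² = 23 gives SD = 10.46 s. It is used below only as a scale. It is not evidence of how the chronometer was run.

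**4. Shift in medians, (a) against (b).** Suppose failures are unrelated to speed and all land in the upper tail. The arm median then moves to the 0.5/0.883 = 0.566 quantile of the per-attempt times in one arm and to 0.5/0.85 = 0.588 in the other. With normal times, the shift in the group difference is 10.46 × (0.223 − 0.167) = 0.6 s. Simulation gave 0.5–1.0 s across scenarios, and about 0 for (c) against (b). If slow patients fail more often (log-normal times, correlation 0.7 between failure and time), the difference in medians was 9.2 s for (c), 9.3 s for (b) and 10.4 s for (a), so (a) and (c) are 1.2 s apart.

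**5. Shift in means, (a) against (b).** (0.15 − 0.117) × added time = 0.033 × 30 = 1.0 s, or 0.033 × 120 = 4.0 s. Simulated shifts were about 1–5 s. The plan reports medians and quartiles.

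**6. Test results.** Mann-Whitney, 23 per arm, SD 10.46 s, failure 11.7% and 15%. Time added per failure under (a) is assumed. Times are normal, except log-normal in the rows with no difference.

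| True difference | Added time | Rejects: (a) / (b) / (c) | Any of the three disagree | (b) and (c) disagree |
|---|---|---|---|---|
| 10 s | 10–60 s | 0.756 / 0.876 / 0.828 | 0.204 | 0.082 |
| 10 s | 30–120 s | 0.690 / 0.871 / 0.810 | 0.257 | 0.093 |
| 10 s | 120–180 s | 0.676 / 0.860 / 0.806 | 0.263 | 0.091 |
| 5.8 s (cited medians) | 30–120 s | 0.340 / 0.426 / 0.379 | 0.265 | 0.115 |
| none | 30–120 s | 0.064 / 0.058 / 0.056 | 0.081 | 0.034 |
| none | 120–180 s | 0.050 / 0.046 / 0.045 | 0.068 | 0.027 |

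No reading inflates type I error materially. In the 10 s rows the running clock costs 12–18 points of power against restart, which makes a difference harder to declare. The two single-attempt readings disagree in about 8–9% of trials in those rows.

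**7. Tube passage time.** With best-view time assumed to be 30–50% of intubation time, a running clock gives about 36–133 s after a failed attempt, against 12–17 s in first-attempt successes. Values that far apart would stand out to anyone handling the data.

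**The case for a change.** The strongest case for a change is that the rule will almost certainly be needed, that the sample size rests on this outcome, and that restart and running clock alone split on significance in 17–27% of trials when a real difference exists. Even if the time belongs to the successful attempt, the text does not cover a later success with another device, or a patient never intubated. Stating the rule would cost almost nothing.

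Part of this stands. The documents do not settle the rule, and a reader of the results should be told which clock was used and how many patients it affected. It does not show that the plan is wrong:

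- Disagreement on p<0.05 is not error. At intermediate power, leaving out or re-timing six observations moves some trials across the threshold under any two sound analyses.
- The figure of about a fifth needs a true difference. It drops to 7–9% without one, and to 11% at a true 10 s difference if only 5% fail in each arm.
- It draws heavily on the running clock, the least natural reading.
- The failure rates come from a mannequin and another GlideScope model. The spread of times and the length of a failed attempt are assumptions.
- No better main analysis emerges. Ranking failures worst can reject on failures alone when times are equal.

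**Conclusion.** The gap is genuine but it is missing detail, and no change to the plan follows. The natural way to fill it is to time the successful attempt and take best-view time from that same attempt, which agrees with the names and definitions the plan already uses. About 6 of 46 patients are affected at the cited rates. Every reading holds type I error near 5%. Median differences move by about 1 s or less (1.2 s at most between the running clock and leaving failures out), while means on a running clock could move by about 1–5 s. The primary outcome, intubation success, does not depend on the choice. Attempt counts were recorded, so the number affected can be shown when results are reported.

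This rests on mannequin failure rates, a back-solved SD of 10.46 s (15 s was also tried, with 21–29% disagreement) and assumed failed-attempt durations of 10–180 s. Much higher failure rates in infants would make the choice matter more, and the recorded attempt counts would show that.
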